5.5.2.3. Rationale for Control Groups

Placebo Control Group

The use of a randomized placebo control group added to established standard of care provides the best scientific evidence of efficacy and safety. The use of a placebo control provides a concurrent comparator group, accounting for not only a placebo effect but a standard of care effect. Notably, accounting for the standard of care effect is critical when designing an outcome-based study conducted globally when there are regional differences in the treatment of subjects with PBC.

Historical Control Group

The available robust historical PBC observational datasets (UK-PBC and Global PBC Study Group) will also be leveraged to provide further comparative evaluation of the clinical benefit of OCA. Each database includes >6000 patients with long-term follow-up.

Comparison of OCA treatment to the historical controls may provide utility in addressing potential bias or confounds associated with the placebo arm. For example, bias associated with the potential addition of commercial OCA and/or differences in long-term standard of care between the treatment arms including ancillary treatments and diagnostics.

Therefore, further evaluation of the effect of OCA will compare OCA treatment versus historical controls, and will be supportive to placebo comparisons (ie, comparisons to historical and placebo controls will be evaluated separately).

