13.1.8. Supportive Analysis

Per the International Conference on Harmonisation (ICH) E10 guidance, “where no obvious single optimal external control exists, it may be advisable to study multiple external controls”. In order to address the risks associated with the inclusion of a long-term placebo arm, supportive analyses of the primary endpoint will compare clinical outcomes in the OCA treatment arm to historical controls, which serves as an external control for supportive analysis.

In an attempt to avoid the inherent biases with historical controls and to maintain the integrity of this comparison, one can invoke matching methods to optimize comparability and find a historical control that is “similar” to a participating subject. The historical database control should be as similar as possible to the study population and should have been exposed to a similar standard of care (see [Section 5.5.2.3](#)).

A propensity score can be used to reduce bias through matching, stratification, regression adjustment, or some combination. Propensity scores use information from a pool of patients who do not participate in the study (historical controls) to identify what would have happened to participating subjects in the absence of the treatment. By comparing how outcomes differ for treated subjects relative to historical controls, it is possible to estimate the effects of the treatment between the treated subjects and the matched natural history subjects.

A full range of covariates across which the treatment and historical controls might differ will be considered to mitigate potential bias. Although the results of using matching controls are conditional only on the observed covariates, if one has the ability to measure many of the covariates that are believed to be related to the treatment assignment, then one can be fairly confident that approximately unbiased estimates for the treatment effect can be obtained. Both UK-PBC Group and the Global PBC Study Group formally collect numerous covariates that could be used for propensity score estimation including standard of care, eg, UDCA.

Historical controls will be chosen based on the same inclusion/exclusion criteria where possible. Propensity scores will be estimated using the available covariates that predict receiving the treatment. Only covariates and not outcome variables will be included in the propensity score estimation, to avoid biased results that are in favor of one treatment.

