The covariates and factors collected in the historical databases will be specified in the SAP.

Propensity scores will be estimated first through a logistic regression model with treatment group as the dependent variable and the above covariates/factors as independent variables. Then the stratum boundaries are determined based on the propensity score values for both groups (OCA population and control [historical and randomized placebo]) combined or in the OCA population or historical control group alone. Based on recommendations in the literature, quintiles of the estimated propensity score from the combined group will be used to determine the stratum boundary cut-offs for the different strata.

The baseline characteristics between treated and natural history subjects in the matched dataset will be summarized and presented in a tabular format. Statistical methods such as Wilcoxon Rank-Sum test will be used to assess the balance for baseline covariates. The standardized difference and variance ratios for these covariates will also be calculated. In addition, box plots of propensity scores for treated and natural history subjects will be separately presented, to further assess the adequacy of matching.

A third-party statistician(s) will perform the propensity score modeling and matching. This third-party statistician(s) will be separate and independent from the statistician(s) who will assess the success of matching and perform efficacy analyses. Outcome events collected in the historical database are: death (liver-related and all-cause), liver transplant, HCC, and other. Other is defined as cirrhosis or decompensation such as ascites, variceal bleed, and encephalopathy.

The propensity score quintile will be then be used as the stratification factor in the stratified log rank test to compare randomized OCA-treated subjects in the ITT population and historical controls (Overall Historical Control Population: both the UK-PBC Group and Global PBC Study Group databases) on the following outcomes:

- Time to death (all-cause)
- Time to liver-related death
- Time to liver transplant
- Time to liver transplant or death (all-cause)
- Time to liver transplant or liver-related death

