13.1.8	
Supportive Analysis
 
Although the results of using matching are conditional only on the observed covariates, if one has the ability to measure many of the covariates that are believed to be related to the treatment assignment, then one can be fairly confident that approximately unbiased estimates for the treatment effect can be obtained.
	
Supportive Analysis
 
Although the results of using matching controls are conditional only on the observed covariates, if one has the ability to measure many of the covariates that are believed to be related to the treatment assignment, then one can be fairly confident that approximately unbiased estimates for the treatment effect can be obtained.

13.3	
Data and Safety Monitoring Committee
 
The DSMC will review data on a periodic basis to ensure the safe and proper treatment of subjects. Based on review of these data, the DSMC will advise the Sponsor on the validity and scientific merit of continuing the study. In addition, the DSMC statistician will evaluate the sample size as described in Section 13.1.2.1.
 
The DSMC operates under an appropriate charter (in compliance with relevant regulatory guidance) that defines its organization and operation and includes specific procedures for each study. The DSMC will prepare written minutes of both its open and closed sessions for each study.
	
Data and Safety Monitoring Committee
 
The DSMC will review data on a periodic basis to ensure the safe and proper treatment of subjects. Based on review of these data, the DSMC will advise the Sponsor on the validity and scientific merit of continuing the study.
 
The DSMC operates under an appropriate charter (in compliance with relevant regulatory guidance) that defines its organization and operation and includes specific procedures for each study. The DSMC will prepare written minutes of both its open and closed sessions for each study. The DSMC will document details about any unblinded subject data reviews in the closed session DSMC minutes, which will be made available to the Sponsor only after the database is locked and the trial is unblinded. Cases of premature unblinding, as noted above, will also be reviewed by the DSMC.

Section	Original Text	Revised Text

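### Section 13.1.8 is too confident that many measured covariates make the OCA-versus-historical estimate approximately unbiased, and the protocol specifies no randomized-placebo-versus-historical comparison that could show residual bias

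*Protocol*

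**What the plan says.** The current text of protocol section 13.1.8 opens the relevant sentence with a caveat, "Although the results of using matching controls are conditional only on the observed covariates". It then says that if many of the covariates thought to relate to treatment assignment can be measured, "then one can be fairly confident that approximately unbiased estimates for the treatment effect can be obtained". The next sentence treats that condition as largely met, saying that both registries "formally collect numerous covariates that could be used for propensity score estimation including standard of care, eg, UDCA". (The Appendix D amendment log carries the same words; the text that counts is 13.1.8.)

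On selection, 13.1.8 states: "Historical controls will be chosen based on the same inclusion/exclusion criteria where possible". Section 13.1.1.1 states the same rule without the qualification. On checking the match, 13.1.8 says: "Statistical methods such as Wilcoxon Rank-Sum test will be used to assess the balance for baseline covariates". It adds standardized differences, variance ratios and box plots of the propensity scores. Sensitivity analyses use each registry alone, and other algorithms are optional.

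The planned analysis is a "stratified log rank test to compare randomized OCA-treated subjects in the ITT population and historical controls", by propensity quintile, on five outcomes built from death and liver transplant. Section 5.5.2.3 gives the purpose, which includes addressing "bias associated with the potential addition of commercial OCA and/or differences in long-term standard of care between the treatment arms", and says that "comparisons to historical and placebo controls will be evaluated separately".

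Two further places matter. Section 13.1.1 requires the historical populations to have shown comparability with the randomized subjects in disease progression as well as in patient characteristics. The end of 13.1.8 allows a revised primary analysis of OCA against placebo and historical controls together, subject to regulatory agreement.

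**The concern.** A propensity score balances what was measured. Approximate unbiasedness needs, in addition, that no important unmeasured factor separates the groups, and a long list of covariates does not establish that. Here the contrast is trial entry against registry membership. The groups may differ in how people came to volunteer, in how fully the exclusions can be applied, in era and in follow-up. The listed checks look only at measured baseline variables, so they cannot show what remains.

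The trial holds subjects who can help. Randomized placebo subjects passed the same entry criteria and have the same visit schedule as the OCA arm. Commercial OCA aside, their hazard ratio against the same historical controls should be near 1 if the method works. The protocol specifies no such comparison.

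At stake is a stated secondary objective (6.2). If trial participants have a better prognosis than matched registry patients, that difference would appear as an OCA effect. The same gap affects pooling: nothing planned would first show that the two control sources agree.

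**Working it through.** **1. The plan's own figures.** Inputs from 13.1.2: placebo survival 0.6 at 8 years, hazard ratio 0.60, 4 years of accrual plus 6 of follow-up, 1:1 allocation, 10% dropout, 127 events, 80% power, 428 subjects.

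- Hazards: placebo -ln(0.6)/8 = 0.0639 per year; OCA 0.6 x 0.0639 = 0.0383.
- Event probability averaged over 6 to 10 years: placebo 0.398, OCA 0.263, mean 0.331.
- 127/0.331 = 384, and 384/0.9 = 427, against 428 stated.
- With the two interim looks, 127 events give 81.3% power by Schoenfeld's formula.
- Expected events: 214 x 0.9 x 0.398 = 77 on placebo and 214 x 0.9 x 0.263 = 51 on OCA.

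The figures reproduce, and none is disputed.

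**2. Illustration on transplant or death.** The protocol gives no event count for this outcome, so these inputs are assumptions: 25 to 45 OCA-arm events (d), control events at r = 1 to 4 times that number at equal risk, no OCA effect, and one unmeasured prognostic factor.

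- Apparent HR = (1 + p_trial(HR - 1)) / (1 + p_registry(HR - 1))
- SE of log HR = sqrt(1/d + 1/d_control), with d_control = r x d / apparent HR
- Chance of a false result favouring OCA = 1 - Phi(1.96 - |ln apparent HR| / SE)

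| Unmeasured factor | Prevalence, trial / registry | Apparent HR | False result favouring OCA (nominal 2.5%) |
|---|---|---|---|
| HR 2 | 20% / 35% | 1.20/1.35 = 0.89 | 6-11% |
| HR 3 | 20% / 40% | 1.40/1.80 = 0.78 | 15-34% |

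Ends of the second row:
- d = 25, r = 1: SE = sqrt(1/25 + 1/32.1) = 0.267, z = 0.251/0.267 = 0.94, giving 15%.
- d = 45, r = 4: SE = sqrt(1/45 + 1/231.4) = 0.163, z = 1.54, giving 34%.

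**3. What the placebo check could show on the same counts.** With no bias, its 95% CI is a factor exp(1.96 x SE) either side: exp(1.96 x sqrt(2/25)) = 1.74 at worst and exp(1.96 x sqrt(1/45 + 1/180)) = 1.39 at best. With no OCA effect the two arms are exchangeable, so the chance that placebo versus historical flags a bias equals the chance that OCA versus historical is misled by it: 15-34% at 0.78 and 6-11% at 0.89. Even at best, the interval around 0.78 runs from about 0.57 to 1.07. An estimate must be below about 1/1.39 = 0.72 (best) or 1/1.74 = 0.57 (worst) to stand clear of 1.

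**4. Other assumptions.** This uses the larger primary-endpoint counts, with historical events at 1 to 20 times 77. It is optimistic, because the five outcomes will have fewer events.

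| Residual HR, trial vs registry | False result favouring OCA |
|---|---|
| 0.9 | 9-14% |
| 0.8 | 26-42% |
| 0.7 | 54-76% |

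The placebo check then has a 95% CI of a factor 1.27 to 1.41. At 0.7 the upper limit is at most 0.7 x 1.41 = 0.99. At 0.8 it is still 0.8 x 1.28 = 1.02 with the largest historical sample. Large bias becomes visible; 0.8 to 0.9 does not reliably do so.

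**The case against.** The strongest reply has five parts.

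- **The limitation is disclosed.** The sentence begins by conceding dependence on observed covariates and says only that one can be fairly confident. This stands against any reading that unbiasedness is asserted outright. It does not rescue the inference, because the conclusion still goes beyond what the concession allows.
- **The analysis is supportive.** It lies outside the testing hierarchy of 13.1.10, so the 2.5% above is a yardstick and not an error rate that the trial promises. This stands.
- **The SAP may contain the check.** It is not at hand and may say how comparability in progression is shown. So the claim is only that this protocol specifies no such comparison. The confident sentence and the list of comparisons are protocol text.
- **Some bias sources are limited.** Section 13.1.1.1 applies the eligibility criteria without qualification, 7.1 describes the historical groups as both concurrent and retrospective, the outcomes are death and transplant, and an independent statistician does the matching. These points reduce the worry but do not test it, and 13.1.8 itself keeps the qualification on eligibility.
- **The check is weak and not clean.** By the figures above it would usually miss a hazard ratio of 0.8 to 0.9, and commercial OCA may contaminate the placebo arm. Both stand and must be stated with the result.

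**Conclusion.** The point holds in limited form. Section 13.1.8 overstates what propensity methods deliver against an external database. Its listed checks cannot show unmeasured differences, and no randomized-placebo-versus-historical comparison is specified despite the comparability requirement in 13.1.1 and the pooling option in 13.1.8. The size depends wholly on assumed residual bias and event counts: from about 6% false support at a residual hazard ratio of 0.89 to about 34% at 0.78 in the transplant-or-death illustration.

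Three stronger readings are not supported:

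- A reader might infer that 5.5.2.3 forbids the check by evaluating the control sources separately. It does not, and needs no amendment. Section 13.1.8 already brings placebo together with historical controls when it sets stratum boundaries and in the possible revised primary analysis.
- A reader might want OCA versus historical to be read only relative to placebo versus historical. That ratio is roughly OCA versus placebo: the historical data largely cancel, and the commercial-OCA problem returns.
- A reader might take a null placebo-versus-historical result as clearance. On these counts it would not be.

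This is a cheap improvement to a supportive analysis and leaves the sample size and the planned primary analysis unchanged.

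**What to change.** In 13.1.8:

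1. Replace the sentence on approximately unbiased estimates with a statement that the comparison adjusts for observed covariates only and that bias from unmeasured differences between trial participants and registry patients may remain.
2. Add randomized placebo versus the matched historical controls, using the same propensity model, quintile strata and five outcomes. Run it over all follow-up and again with placebo follow-up censored at the start of commercial OCA, noting that this censoring may be informative.
3. Report that hazard ratio with its confidence interval beside OCA versus historical, and before any pooling of placebo with historical controls in a revised primary analysis.
4. State that precision is limited: the check can expose large bias, but a null result does not exclude a modest one, with a hazard ratio of about 0.8 to 0.9.

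The cost is a few sentences and one extra set of tables from data already held. The downside is that the supportive claim may come out weaker.

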APPENDIX E. SUMMARY OF CHANGES: PROTOCOL AMENDMENT 1.1 (DATED 12 NOV 2015)

Rationale

The changes to Amendment 1 of the protocol, detailed below, generated specifically for regulatory authority requests, include an additional exclusion criteria and changes to text precluding UDCA naïve subjects from entering the study and clarifying information showing that OCA may increase the exposure of narrow therapeutic index drugs that are substrates for CYP1A2, thus answering questions raised by regulatory authorities.

Summary of Changes

The following revisions were made to protocol 747-302 under Amendment 1.1. (Note: Revised text in Amendment 1.1 is indicated in bold font, and the text deleted from Protocol Amendment 1 is crossed out in the table below. Minor formatting changes are not listed.)

Section	Original Text (Amendment 1, 29 April 2015)	Revised Text (Amendment 1.1, 12 November 2015)
Title Page	Original: 03 October 2014 Amendment 1: 29 APRIL 2015	Original: 03 October 2014 Amendment 1: 29 April 2015 Amendment 1.1: 12 November 2015
Study Personnel Contact Information	Mobile: PPD (Pacific time zone) Telephone: PPD Telephone PPD	(deleted) Telephone: PPD (deleted)
Synopsis, Exclusion Criteria	(insertion)	14. UDCA naïve (unless contraindicated)
Synopsis, Statistical Methods: Sample Size Justification	
 5% of the subjects will have never been treated with UDCA; 95% of the subjects will have been on UDCA for at least 1 year 	(deleted)
8.3 Subject Exclusion Criteria	(insertion)	14. UDCA naïve (unless contraindicated)
9.2 Concomitant Medications	(insertion)	The effect of OCA on drug metabolizing enzymes has been evaluated in both in vitro and clinical studies. The PK profile

Section	Original Text (Amendment 1, 29 April 2015)	Revised Text (Amendment 1.1, 12 November 2015)
		
of caffeine, a sensitive CYP1A2 substrate, showed weak effect of OCA on CYP1A2. Based on these results, OCA may increase the exposure of narrow therapeutic index drugs that are substrates for CYP1A2, such as theophylline and tizanidine.

12.1.4.2 Reporting of Serious Adverse Event
	
Mobile: PPD (Pacific time zone) [contact]
	
(deleted) Telephone: PPD

13.1.2 Determination of Sample Size
	
5% of the subjects will have never been treated with UDCA; 95% of the subjects will have been on UDCA for at least 1 year
	
(deleted)

APPENDIX F. SUMMARY OF CHANGES: PROTOCOL AMENDMENT 1.1 TO VERSION 3 (DATED 07 SEP 2016)

Rationale

The changes to Version 3 of the protocol, include dosing adjustments based on Child-Pugh scoring, additional exclusion criteria, changes to text precluding UDCA-naïve subjects from entering the study.

Please note that the Sponsor has renamed protocol “amendments” to “versions”, therefore all future revisions that require a revised protocol will have an associated “version” number. The table below includes substantial revisions made to Protocol 747-302 under Version 3, which encompass the revisions captured in Protocol Amendment 1.1. Revised text in Version 3 is indicated in bold font, and the text deleted from Protocol Amendment 1.1 is crossed out in the table below. (Minor/editorial changes and non-substantial changes are not listed individually in the summary table below).

Section	Original Text (Amendment 1.1, 12 November 2015)	Revised Text (Version 3, 07 September 2016)	Justification for Change
Synopsis, Methodology	
... Mean values for ALP and total bilirubin will be calculated using all available screening values. Subjects who meet all inclusion criteria and none of the exclusion criteria will be randomized (1:1) to OCA or placebo treatment groups. The randomization will be stratified by ursodeoxycholic acid (UDCA) treatment (yes/no) and baseline bilirubin categories (>upper limit of normal [ULN]/ ≤ULN).
 
Investigational product (OCA or matched placebo) will be taken orally, once daily. Investigational product will be initiated at 5 mg OCA or matched placebo. After 3 months of treatment with investigational product, the dose may be increased (to the maximum dose of 10 mg OCA or matched placebo, in a blinded manner) at the 3-month visit or any subsequent study visit based on tolerability. Subjects will be seen at quarterly visits for the duration of the study.
	
... Investigational product will be taken orally, once daily for the majority of subjects; dose and frequency will be modified for subjects with cirrhosis (including subjects progressing to cirrhosis during the study) and classified as Child-Pugh B or C. The randomization will be stratified by ursodeoxycholic acid (UDCA) treatment (yes/no) and baseline bilirubin categories (>upper limit of normal [ULN]/ ≤ULN).
	
To incorporate a dosing and titration regimen based on subject’s Child-Pugh Scores, to align with the recommended dosing regimen found in the Ocaliva US Package Insert for patients with hepatic impairment.

Section	Original Text (Amendment 1.1, 12 November 2015)	Revised Text (Version 3, 07 September 2016)	Justification for Change

Synopsis, Methodology. 7.1.1, Study Design Diagram, Figure 1
	
Schematic diagram
	
Updated schematic diagram
 
Initial dose titration of investigational product should occur at the Month 3 visit, or any study visit thereafter for subjects on all dosing regimens, based on tolerability. Subsequent dose titration(s) for subjects classified as Child Pugh B or Child-Pugh C and following a modified dosing schedule may occur no earlier than 6 weeks after the previous dose titration
	
Incorporate updated dosing scheme to reflect addition of Child-Pugh scoring.

Section	Original Text (Amendment 1.1, 12 November 2015)	Revised Text (Version 3, 07 September 2016)	Justification for Change
Synopsis, Methodology	(insertion)	
Dosing frequency will be determined by the presence or absence of cirrhosis and, if cirrhosis is present, by Child-Pugh Score as described below:
 
 • Non-cirrhotic subjects or subjects classified as Child-Pugh A at screening will receive 5-mg OCA or matching placebo once daily for 3 months. Subjects should titrate to a maximum dose of 10-mg OCA once daily (or matching placebo) at the Month 3 visit or at any study visit following the Month 3 visit based on tolerability of the product. • For those subjects that up-titrate to 10 mg, dosing may be decreased to 5 mg at any time during the study as considered clinically appropriate (eg, based on tolerability). Subjects may be titrated back to a maximum dose of 10 mg once daily based on tolerability and clinical judgment of the Investigator. • Subjects who are cirrhotic and classified as Child-Pugh Class B or Child-Pugh Class C will initiate a modified treatment regimen with 5-mg OCA or matching placebo once weekly for at least 3 months. Subjects classified as Child-Pugh Class B should eventually titrate to a maximum dose of 5-mg OCA or matching placebo once daily, based on tolerability. Subjects classified as Child-Pugh Class C should titrate to a maximum dose and frequency of 10-mg OCA or matching placebo twice weekly, based on tolerability. 
Includes New Table: Planned Dosing Regimen by Cirrhosis and Child-Pugh Score
	Revised methodology to incorporate the changes in dosing for subjects based on the Child-Pugh Scores.
5.1, Overview	(insertion)	
The United States Food and Drug Administration (FDA) has granted accelerated approval for Ocaliva for the treatment of PBC. Ocaliva is not yet approved outside the United States for use in any indication.
	Language updated as OCA is approved in the US with the trade name Ocaliva.


5.5.2.2, Rationale for Modified OCA Doses in Patients Classified with Child-Pugh B or Child-Pugh C Hepatic Impairment
	
(Insertion)
	
New section: Rationale for Modified OCA Doses in Patients Classified with Child-Pugh B or Child-Pugh C Hepatic Impairment
 
Simulations using a physiologic PK model predicted changes in systemic and liver OCA concentrations associated with changes in the severity of hepatic impairment (Child-Pugh score). Model simulations predicted that for mild (Child-Pugh A), moderate (Child-Pugh B), and severe (Child-Pugh C) hepatic impairment, total OCA plasma concentrations increase 1.4-, 8.0-, and 13-fold relative to subjects with normal hepatic function, whereas total OCA liver concentrations increase 1.1-, 1.5-, and 1.7-fold, respectively.
 
Because the liver is the primary site of action for the safety and efficacy of OCA, it is important to account for the differences in systemic and liver exposure when assessing effective doses. It is also important to note that while hepatically-impaired (Child-Pugh B and C) subjects treated with OCA in phase 1 and 2 studies experienced plasma OCA exposures >10-fold higher than those in healthy subjects, no apparent impact on the overall safety profile was observed, consistent with only a modest increase in liver exposure of OCA associated with hepatic impairment. Collectively, the results from these analyses and those from bile acids in the literature suggest that the doses of OCA administered to hepatically-impaired patients should be modestly lower than those for patients with normal hepatic function to achieve similar hepatic exposure.
 
Per the approved FDA prescribing label, the recommended dosing regimen for OCA in subjects with moderate and severe hepatic impairment is a starting dose of 5-mg OCA once weekly. Dosage adjustments in subjects with moderate (Child-Pugh B) or severe (Child-Pugh C) hepatic impairment may be made after establishing tolerability at the lower dose
	
Provide the rationale to incorporate a dosing and titration regimen based on subject's Child-Pugh Scores into the protocol.

--	--------------------	--	--

Section	Original Text (Amendment 1.1, 12 November 2015)	Revised Text (Version 3, 07 September 2016)	Justification for Change
		(full modified dosing regimen is described in Appendix A).	
5.6, Summary of Known Potential Risks with OCA	(Insertion)	...These findings were seen more frequently with doses above 10 mg OCA. In addition, cholecystitis, including acute cholecystitis, was reported in association with treatment with OCA.	Added two AE terms reported in the updated Investigator’s Brochure.
7.1, Overall Study Design	
...Investigational product will be initiated at 5 mg OCA or matching placebo.
 
Following 3 months of treatment with investigational product, subjects should be titrated in a blinded manner (ie, subjects randomized to OCA will increase their dose to 10 mg OCA) based on tolerability
	
Investigational product will be taken orally, once daily. Subjects who are non-cirrhotic or classified as Child-Pugh A at Screening will initiate investigational product once daily with 5-mg OCA or matching placebo. Following 3 months of once daily treatment with investigational product, the dose should be titrated to a maximum 10 mg OCA or matching placebo once daily, based on tolerability (see Section 7.3).
 
Subjects with cirrhosis and classified as Child-Pugh Class B or Child-Pugh Class C will follow a modified dosing regimen, and will initiate investigational product once weekly with the 5-mg OCA or matching placebo dose. In addition, these subjects will follow a modified titration plan, which is outlined in Appendix A.
	Amend the protocol to incorporate a dosing and titration regimen based on subject’s Child-Pugh Scores.
7.1.2, Table 1, Schedule of Study Procedures – Screening to Month 12 (Table 1 of 2), 9.3, Treatment compliance	Safety Contact	This visit has been deleted.	Replaced with the 1 Month Post-Titration Visit.
	(Insertion)	
Added the following visits:
 
 • Month 1 • 1 Month Post-Titration Visit 	Visits were added to accommodate the updated dosing and titration regimen based on subject’s Child-Pugh Scores.

Section	Original Text (Amendment 1.1, 12 November 2015)	Revised Text (Version 3, 07 September 2016)	Justification for Change
	
^bThe subject should be contacted by telephone on a monthly basis in between at-elinic study visits at Month 1 and Month 2 (\pm 1 week), and also 2 weeks post dose titration (up or down), to assess for AEs and concomitant medications and to verify that s/he is dosing as directed.
 
^eAs soon as possible upon study discontinuation and as near as possible to last dose taken.
 
ⁿSubject to begin dosing on Day 1
	
Deleted.
	
Result of table being updated for the dosing and titration regimen based on subject’s Child-Pugh Scores.

	
(Insertion)
	
Added the following study procedures:
 
 • Cirrhosis Status Assessment^c • Assessments for Child-Pugh Scores^g • Dose Titration: Standard Dosing^{n,o} • Dose Titration: Modified Dosing^{n,o} • Dosing Diary 	
Study procedures were added to accommodate the updated dosing/titration regimen. Dosing diary was added to improve compliance.

	(Insertion)	
Added the following footnotes:
 
 • ^bSafety Post-Titration visits must be performed 1 month + 1 week after any up-titration in dose and/or frequency in subjects following modified dosing due to Child-Pugh B and Child-Pugh C hepatic impairment. In subjects following the standard dosing regimen, the post-titration visit must be performed only after the first up-titration to 10 mg OCA or matching placebo, or after ≥ 3 months at a decreased dose or frequency. • ^cPresence or absence of cirrhosis should be assessed per Section 9.7.3. Cirrhosis status should be repeated as clinically indicated. • ^fMayo Risk Score will be calculated based on central laboratory evaluations, diuretic use data, and peripheral edema assessment data captured in the CRF. • ^gChild-Pugh Score will be calculated based on ascites assessment, hepatic encephalopathy grade, and central laboratory evaluations per the Child-Pugh scoring system noted in the eCRF. • ⁿPre-titration tolerability assessment, which include a review of AEs and a review of safety laboratory results (eg, chemistry, hematology, and coagulation), must be completed by the Investigator before any up-titration can occur as defined in Section 7.4.1. Lab results obtained within 2 months prior to any up-titration may be used for assessment. • ^oDose Titration is based on cirrhosis status (Section 9.7.3) and Child-Pugh score (Section 7.3). The initial dose titration of investigational product may occur at the Month 3 visit, or any study visit thereafter for subjects on all dosing regimens, based on tolerability. Subsequent dose titration(s) for 	
Added footnotes provide clarity regarding assessments and visits based on the evaluation of Child-Pugh scores.

--	-------------	---	---

Section	Original Text (Amendment 1.1, 12 November 2015)	Revised Text (Version 3, 07 September 2016)	Justification for Change
		
subjects who are classified as Child-Pugh B or Child-Pugh C and following a modified dosing schedule may occur no earlier than 6 weeks after the previous dose titration. For complete modified dose titration criteria, refer to Appendix A.
 
 • ^PSubjects will be instructed to begin dosing on the day after the Day 0 visit (ie, on Day 1) and to take investigational product at approximately the same time of day. Subjects must be instructed to swallow the tablet whole; they must not chew, divide, or crush the tablet. 	
7.1.2, Table 2, Schedule of Study Procedures – Year 2 Through End of Study (Table 2 of 2)		
New table- Schedule of Study Procedures – Year 2 Through End of Study (Table 2 of 2)
	
Divided Schedule of Study Procedures into 2 tables, updated to include visits added per updated dosing/titration information.

Section	Original Text (Amendment 1.1, 12 November 2015)	Revised Text (Version 3, 07 September 2016)	Justification for Change
7.3, Planned Dosing Regimen	
7.3 Treatment Assignment Subjects will receive either placebo or 5 mg OCA and should titrate to 10 mg OCA (in a blinded manner) at the 3 month study visit or at any study visit thereafter depending on tolerability.
	
7.3 Planned Dosing Regimen Subjects will be randomized to treatment with either OCA or matching placebo in a 1:1 ratio. Subjects will be dosed according to their cirrhosis status (as defined in Section 9.7.3) and applicable Child-Pugh Score (see Section 9.7.4) as outlined in Table 3. Subjects who are non-cirrhotic or classified as Child-Pugh A at screening will receive 5-mg OCA or matching placebo once daily for 3 months. Subjects should titrate to a maximum dose of 10-mg OCA once daily (or matching placebo) at the Month 3 visit or at any study visit following the Month 3 visit based on tolerability of the product. A review of safety laboratory results (eg, chemistry, hematology, and coagulation) obtained no more than 2 months prior to the planned up-titration visit must be completed as part of the product tolerability assessment before up-titration can occur (see Section 7.4.1). For those subjects that up-titrate to 10 mg, dose may be decreased to 5 mg at any time during the study as considered clinically appropriate (eg, tolerability). Subjects may be titrated back up to a maximum dose of 10 mg once daily based on tolerability and clinical judgment of the Investigator. A review of safety laboratory results obtained within 2 months of the planned up-titration visit date is not required prior to re-challenging a subject up to 10 mg once daily dosing, as long as the decrease in dose/dosing frequency was less than 3 months in duration.
	
Section renamed to reflect changes in titration and dosing for subjects with hepatic impairment.

	(Insertion)	
New: Table 3: Planned Dosing Regimen by Cirrhosis and Child-Pugh Score New: Table 4: Determination of Dosing Regimen
	
Tables added to clarify changes in titration and dosing.

Section	Original Text (Amendment 1.1, 12 November 2015)	Revised Text (Version 3, 07 September 2016)	Justification for Change
7.4 Dose Titration Criteria	
After 3 months of treatment at the 5 mg dose, the dose of OCA will be increased to the maximum dose of 10 mg OCA or matched placebo (in a blinded manner) at the 3 month visit or any study visit following the 3 month visit based on tolerability of investigational product.
 
For those subjects that increased their dose to 10 mg, they may decrease his or her dose to 5 mg at any time during the study as considered appropriate (eg, tolerability), but should be titrated back to 10 mg based on tolerability and clinical judgment by the Investigator as soon as possible with the goal that all subjects remain on the 10 mg dose if tolerated
	
Dose titration may follow the scheduled dosing regimens described in Section 7.3 or occur due to tolerability concerns or as a result of changes in a subject’s cirrhosis status (using histology or non-histological methods as defined in Section 9.7.3 and Section 9.7.4) or Child-Pugh Score.
 
Scheduled Dose Titration - The first dose titration for any subject may occur no earlier than 3 months following initiation of OCA or matching placebo. Subsequent titrations in dose or dosing frequency for subjects following the Modified Dosing Regimens may occur no earlier than 6 weeks (via an unscheduled visit or regular visit- see Appendix A) following an up-titration.
 
Tolerability Dose Titration - Investigators may decrease the dosing frequency or dose for any subject at any time during the study, as considered clinically appropriate (eg, tolerability; see Section 7.4.2).
 
Dose Titration due to Change in Cirrhosis or Child-Pugh Score - When subjects demonstrate a change in cirrhosis status (as assessed per Section 9.7.3) or Child-Pugh Score (Section 9.7.4), dosing should be reassessed and the dosing regimen modified appropriately. Changes to the dosing regimen are not mandatory and should be based on clinical judgment as well as change in cirrhosis status. Table 5 provides an overview of the possible changes in dosing regimen due to changes in cirrhosis or Child-Pugh Score. Dosing should follow the titration schedule of the new dosing regimen such that the maximum dose within that dosing regimen is ultimately attained, based on tolerability and clinical judgment.
	
Entire section revised to reflect changes in titration and dosing.

